10.2 Populations for Analyses

The following defined populations will apply to pooled tumor types unless otherwise specified:

Population	Description
Enrolled participants	All participants who signed an informed consent form and were registered into the IVRS.
Randomized participants	All participants who were randomized.
Treated participants	All participants who received at least 1 dose of nivolumab or ipilimumab.
Pharmacokinetics participants	All treated participants with available serum time-concentration data.
Immunogenicity participants	All treated participants with baseline and at least 1 post-baseline immunogenicity assessment.

The primary endpoint of the trial is BICR-assessed ORR in the tTMB high population and the bTMB high population in a salvage setting (Table 10.2-1).

Table 10.2-1: Timing of Analysis and Primary Populations for Primary Endpoint

Analysis	Timing	Primary Population to be Used for Primary Endpoint
bTMB interim analysis	Approximately the first 30 randomized participants in the nivolumab + ipilimumab arm with bTMB \geq 10 mut/Mb at baseline have been randomized and followed for at least 6 months	All bTMB high randomized participants (followed for at least 6 months)
bTMB final analysis	At least 12 months after approximately 76 bTMB high participants are treated in the nivolumab + ipilimumab arm and study randomization is completed	All bTMB high participants randomized prior to the closure of the bTMB high population in Dec-2019
tTMB interim analysis	Approximately the first 50 randomized participants in the nivolumab + ipilimumab arm with tTMB \geq 10 mut/Mb at baseline have been randomized and followed for at least 12 months and study randomization is completed	All tTMB high participants randomized at least 12 months prior to the LPLV for the analysis
tTMB final analysis	At least 12 months after all tTMB \geq 10 mut/Mb participants have been randomized	All tTMB high randomized participants

10.3 Statistical Analyses

Unless otherwise specified, all analyses will be performed for all randomized participants in the salvage setting by treatment group as randomized and for tTMB and bTMB populations separately within each treatment group.

Demographic and baseline laboratory results will be summarized using descriptive statistics for all randomized participants. Baseline characteristics, including demographics (age, gender, geographic location, race/ethnicity) and clinical characteristics (date of diagnosis, disease stage, liver function status, performance status, co-morbidity/prognostic indicators, location of metastases) will be collected at the time of treatment initiation for each arm. General descriptive statistics, including mean and standard deviation (SD) for continuous variables, count and percentage for categorical variables will be used extensively to examine these variables.

The statistical analysis plan will be developed and finalized before database lock and will describe the selection of participants to be included in the analyses, and procedures for accounting for missing, unused, and spurious data. A summary of planned statistical analyses of the primary and secondary endpoints is in [Sections 10.3.2](#) and [10.3.3](#).

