Procedure	Day 1	Every 2 weeks (i.e. every subsequent cycle Day 1) (± 3 Days)	Every 6 weeks (i.e. every 3 cycles Day 1 (± 3 Days))	Every 12 weeks (i.e. every 6 cycles Day 1) (± 7 Days)	Notes For the purposes of this table, a cycle refers to nivolumab every 2 weeks
Vital signs	X	X			Temperature, blood pressure, and heart rate. Must be performed prior to dosing.
Concomitant medication	Continuously				
Adverse events (including serious and non-serious) assessment	Continuously				Record at each visit. All AEs (SAEs or non-serious AEs), including those associated with SARS-CoV-2 infection, must be collected continuously throughout the treatment period. Adverse events and laboratory values will be graded according to the NCI-CTCAE version 5.
Laboratory Assessments					
Hematology and chemistry	X	X			See Section 9.4.3 Clinical Safety Laboratory Assessments. Must be performed within 72h prior to dosing.
Thyroid function testing	X		X (see note)		Thyroid function testing should be done every 4 weeks (i.e., Day 1 of every other cycle) for the first 10 cycles, and then every 8 weeks until completion of study treatment. Must be performed within 72h prior to dosing.
Pharmacokinetic Assessment	See Section 9.5				
Immunogenicity Assessment	See Section 9.5				
Biomarker assessment	See Section 9.8				
Collection of tumor tissue for biomarkers upon disease progression	See Section 9.8				If a biopsy has been performed and tissue is available, participants are requested to submit fresh tumor tissue for biomarker

Table 2-4: On Study Assessments Treatment Phase – Arm B Rollover – Participants Treated with Nivolumab in Combination with Ipilimumab After Disease Progression During Nivolumab Monotherapy (CA209848)

Procedure	Day 1	Every 2 weeks (i.e. every subsequent cycle Day 1) (± 3 Days)	Every 6 weeks (i.e. every 3 cycles Day 1 (± 3 Days))	Every 12 weeks (i.e. every 6 cycles Day 1) (± 7 Days)	Notes For the purposes of this table, a cycle refers to nivolumab every 2 weeks
					research. Tissue submission is optional and biopsy is not required by protocol.
Additional research collection	See Section 9.8.1				
Efficacy Assessments					
Body Imaging				X (see note)	For Solid Tumors: Tumor Assessments should occur every 12 weeks (± 7 days) until BICR confirmation of disease progression or treatment discontinuation (including treatment beyond progression), whichever comes later. See Section 9.1.1 for further details.

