7.1 Treatments Administered

The selection and timing of dose for each participant is as follows:

Table 7.1-1: Selection and Timing of Dose

Treatment Arm	Study Treatment	Participant Age/Weight	Unit dose strength(s)/ Dosage level(s)	Frequency of Administration	Route of Administration
Arm A or Arm B Rollover: nivolumab in combination with ipilimumab	Nivolumab	Adults and adolescents $\geq 40\text{kg}$	240 mg	Q2 weeks up to 24 months	IV
		Adolescents $< 40\text{kg}$	3 mg/kg	Q2 weeks up to 24 months	IV
	Ipilimumab	All participants	1 mg/kg	Q6 weeks up to 24 months	IV
Arm B: nivolumab monotherapy	Nivolumab	Adults and adolescents $\geq 40\text{kg}$	480 mg	Q4 weeks up to 24 months	IV
		Adolescents $< 40\text{kg}$	6 mg/kg	Q4 weeks up to 24 months	IV

Note: The mention of adolescents is not applicable for sites in Belgium or the Netherlands as adolescent participants will not be included in these countries.

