10.3.2 Safety Analyses

Endpoint Definition	Statistical Analysis Methods

Primary
	
Not applicable

Endpoint Definition	Statistical Analysis Methods
Secondary	
Safety and tolerability	
Descriptive statistics of safety will be presented using the National Cancer Institute (NCI) Common Terminology Criteria for Adverse Events (CTCAE) version 5.0 by tumor types. All on-study AEs and SAEs and drug-related AEs and SAEs will be tabulated using worst grade per NCI CTCAE version 5.0 criteria by system organ class and MedDRA preferred term.
 
On-study lab parameters including hematology, coagulation, chemistry, liver function and renal function will be summarized using worse grade per NCI CTCAE version 5.0 criteria.

Exploratory	Will be described in the statistical analysis plan finalized before database lock

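### Section 10.3.2 neither overrides the as-randomized default nor cuts at rollover, so unless the SAP departs from it, adverse events on nivolumab + ipilimumab after rollover count under monotherapy

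*Combined protocol and SAP*

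**What the plan says.** Section 10.3 sets the default: "Unless otherwise specified, all analyses will be performed for all randomized participants in the salvage setting by treatment group as randomized", and also "for tTMB and bTMB populations separately within each treatment group".

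Section 10.3.2 then describes safety. Its tabulation rule is "All on-study AEs and SAEs and drug-related AEs and SAEs will be tabulated using worst grade per NCI CTCAE version 5.0 criteria". The only grouping it names is the one that closes this phrase: "Common Terminology Criteria for Adverse Events (CTCAE) version 5.0 by tumor types". Laboratory values are also summarized at worst grade. Neither section defines the on-study period.

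Section 10.2 defines a Treated population, "All participants who received at least 1 dose of nivolumab or ipilimumab", but does not assign it to safety. Section 7.4.3.1 lets Arm B participants receive the combination after progression, within one 24-month treatment clock that starts at the first monotherapy dose. Table 2-4, the schedule for the rollover phase, says that adverse events "must be collected continuously throughout the treatment period". For dosing, Table 7.1-1 places rollover with the combination: "Arm A or Arm B Rollover: nivolumab in combination with ipilimumab".

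Section 10.3 also announces a SAP, to be finalized before database lock, that "will describe the selection of participants to be included in the analyses" and will deal with missing, unused and spurious data. That SAP is not in the documents.

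**The concern.** Under an as-randomized grouping, an Arm B participant stays in the monotherapy column after starting ipilimumab. For safety, that attributes events to a regimen the participant was no longer receiving.

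Safety and tolerability is a secondary objective (Section 4), and Section 10.1 gives the monotherapy arm the task of showing what each component contributes. If rollover-phase events sit in the monotherapy column, the two regimens look closer in toxicity than they are. The error leans toward the statement in Section 3.3.1 that their safety profiles at the selected dose are comparable.

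A lesser consequence of the same default is that participants who were randomized but never treated enter the safety denominators.

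**Working it through.** **1. Is the default overridden for safety?** Setting the analyses side by side:

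| Analysis | Population named | What happens at progression or rollover |
|---|---|---|
| Best overall response (10.3.1) | Randomized | Ends at initial progression, by definition of the endpoint |
| Patient-reported outcomes (10.3.4) | Treated, with baseline and a later assessment | Repeated for rollover participants |
| Safety (10.3.2) | None | Nothing stated |

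Presentation by tumor type adds a layer; it does not replace the treatment-group default. Section 10.3.2 therefore overrides neither the population nor the grouping.

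**2. Do rollover events fall inside the tabulated period?** Rollover lies within the study-treatment clock (7.4.3.1). Events are collected throughout it (Table 2-4) and up to 100 days after study drug is stopped (Table 2-5). Read literally, they are on-study events of participants randomized to monotherapy.

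**3. Direction.** Worst grade is a maximum over the participant's window. Extending the window past rollover can leave that maximum unchanged or raise it, never lower it. With a fixed denominator, the monotherapy rates stay the same or go up.

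**4. Denominators.** The plan's own sample size reproduces: 76 + 76 − 76 × 0.40 = 121.6, about 122 on the combination; 1.5 × 122 = 183 in total; 183 / 3 = 61 on monotherapy. At the stated maximum, 342 / 3 = 114. Section 10.3.6 gives 38 on monotherapy per TMB population.

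**5. Size.** Shift in the monotherapy Grade 3/4 rate = k / n, where k is the number of Arm B participants whose first Grade 3/4 event comes after rollover. The documents do not give k; 0, 3 and 6 of 61 are assumptions.

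| k | n | Shift (percentage points) |
|---|---|---|
| 1 | 61 | 1.64 |
| 1 | 114 | 0.88 |
| 1 (a member of that TMB population) | 38 | 2.63 |
| 0 | 61 | 0 |
| 3 | 61 | 4.92 |
| 6 | 61 | 9.84 |

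**6. Upper bound on exposure.** The first scheduled scan is at week 12 (Table 2-3). Taking 24 months as 730.5 days, 730.5 − 84 = 646.5 days, or about 21.2 months (88.5% of the clock). This assumes rollover on the day of that scan. It ignores the mandatory central confirmation of progression (9.1.3.1) and the renewed eligibility check and Medical Monitor discussion (7.4.3.1).

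**7. Never-treated participants.** If u of 61 are never treated, rates are multiplied by (61 − u) / 61: 0.984 for u = 1 and 0.951 for u = 3, a relative fall of 1.6% to 4.9%. The values of u are assumed. Few are expected, since treatment should start within 3 days of randomization (7.1.1, 7.1.2). This effect works in the opposite direction.

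**The case against.** The strongest reply is that the SAP may settle all of this. Section 10.3 calls its own text a summary, and the SAP could name the safety set, define on-study and handle crossover. That stands as far as it makes the consequence conditional: a reader might infer that the trial has misattributed events, and the documents do not show that. It does not remove the point. The deferral in Section 10.3 covers which participants are included and how defective data are handled, not attribution to treatment or the adverse-event window. Within Section 10.3.2, only the exploratory row is sent to the SAP. A SAP that simply followed the protocol would carry the default forward.

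Second, the intent may well be a treated-population analysis. A Treated set exists, non-serious events are collected only from the start of treatment (9.2.1), and Appendix 3 defines an adverse event in someone given study treatment. That is plausible as intent, but none of it is written into the safety analysis.

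Third, the stakes are limited. The monotherapy arm is non-comparative, and the only between-arm quantity in Section 10 is a descriptive interval for the ORR difference. No between-arm safety comparison or safety decision rule is planned. This stands in full.

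Three stronger numerical readings are also tempting and unsupported:

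- A reader might infer a large minimum shift in each tumor-type row from the 15% cap. The cap applies to the total sample (5.2), about 27 of 183. The readable text names TMB and line of therapy as stratification factors (5.4.1, 5.4.2), not tumor type. Arm B's count within one tumor type is therefore not fixed by the cap.
- A reader might apply 3 or 6 participants to n = 38. That would require every one of them to belong to the same TMB population.
- A reader might take 21 of 24 months as typical. It is only a bound.

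**Conclusion.** The point holds in its conditional form. As written, the protocol tabulates post-rollover nivolumab + ipilimumab events at worst grade under nivolumab monotherapy, unless the SAP departs from the stated default. The bias can only keep or raise the monotherapy rates, so it works against the arm's purpose of showing the contribution of components.

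The size cannot be determined, because no rollover share is given; it is zero if no rollover participant reaches a higher grade after rollover. The per-participant shifts above are arithmetic. The range of 0 to 9.8 points rests on the assumed 0 to 6 participants of 61.

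This is a descriptive secondary analysis, and the primary ORR is untouched. It should still be corrected before database lock, because the protocol already shows the remedy in its rule for patient-reported outcomes.

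**What to change.** State the following in Section 10.3.2 and in the SAP:

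> Safety analyses use all treated participants (Section 10.2) by treatment received. Treatment-emergent AE tables cover first dose to 100 days after last dose. Arm B monotherapy tables include only AEs and laboratory results dated before the first rollover dose of nivolumab + ipilimumab. AEs starting or worsening, and laboratory results collected, on or after that dose are tabulated separately as the rollover period. SAEs and SARS-CoV-2 AEs from consent to first dose, those reported after 100 days, and SAEs in never-treated participants are listed.

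This window should not be described as matching Section 9.2.1. That section collects SAEs and SARS-CoV-2 events from consent, and non-serious events for at least 100 days after treatment; the listings cover the difference.

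The documents do not say whether the CRF dates grade changes. If it does not, list the AEs that span the rollover date.

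The cost is wording and one extra set of tables, mostly from data already collected. One downside remains: rollover may begin 22 days after the last monotherapy infusion (7.4.3.1), so some late monotherapy events will fall in the rollover table. If the SAP already contains these rules, only Section 10.3.2 needs aligning. No dosing or clinical rule changes.

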10.3.1 Efficacy Analyses

Endpoint Definition	Statistical Analysis Methods
Primary	

ORR (based on BICR assessments) is defined as the number of participants with a best overall response of confirmed CR or PR divided by the number of all randomized participants. Best overall response is defined as the best response designation, as determined by BICR, recorded between the date of randomization and the date of objectively documented progression (per RECIST v1.1 or RANO criteria) or the date of subsequent therapy, whichever occurs first. For participants without documented progression or subsequent therapy, all available response designations will contribute to the BOR determination. For participants who continue treatment beyond progression, the BOR will be determined based on response assessments up to the time of initial RECIST 1.1 progression.
	
BICR-assessed objective response rate (ORR) using disease specific response criteria: Response Evaluation Criteria in Solid Tumors (RECIST 1.1), and Response Assessment for Neuro-Oncology (RANO) criteria for primary CNS neoplasms.
 
BICR-assessed ORR will be summarized by binomial response rates and their corresponding two-sided 95% exact CIs using Clopper-Pearson method.

Secondary	

DOR (based on BICR assessments) is defined as the time from first confirmed response (CR or PR) to the date of the first documented tumor progression as determined using RECIST 1.1 or RANO criteria or death due to any cause, whichever occurs first.
 
Participants who start subsequent therapy without a prior reported progression will be censored at the last evaluable tumor assessments prior to initiation of the subsequent anticancer therapy. Participants who die without a reported prior progression will be considered to have progressed on the date of their death.
 
Participants who neither progress nor die will be censored on the date of their last evaluable tumor assessment.
	
BICR-assessed duration of response (DOR) will be estimated for all randomized participants who achieve confirmed PR or CR using the Kaplan-Meier (KM) product-limit method. Median values of DOR, along with two-sided 95% CI using Brookmeyer and Crowley method, will also be calculated. Probability of achieving $DOR \geq 6$ months will be calculated using KM method with 95% CI.


The investigator-assessed ORR
	
Investigator-assessed ORR will be summarized by binomial response rates and their corresponding two-sided 95% exact CIs using Clopper-Pearson method.

The investigator-assessed DOR
	
Investigator- assessed duration of response (DOR) will be estimated for all randomized participants who achieve confirmed PR or CR using the Kaplan-Meier (KM) product-limit method. Median values of DOR, along with two-sided 95% CI using Brookmeyer and Crowley method, will also be calculated. Probability of achieving $DOR \geq 6$ months will be calculated using KM method with 95% CI.

TTR is defined as the time from randomization date to the date of the first confirmed response, as assessed by the BICR.
	
Time to response (TTR) will be summarized using descriptive summary statistics for the responders.

Endpoint Definition	Statistical Analysis Methods

CBR is defined as the number of participants with a best overall response (BOR) of confirmed complete response (CR) or partial response (PR) or stable disease (SD) divided by the number of randomized participants.
	
BICR and Investigator assessed CBR will be summarized by binomial response rates and their corresponding two-sided 95% exact CIs using Clopper-Pearson method.

OS is defined as the time from the randomization date to the date of death.
	
Time to event distribution will be estimated using Kaplan Meier techniques. Median OS along with 95% CI will be constructed based on a log-log transformed CI for the survivor function. Rates at some fixed timepoints (6, 12, 18 and 24 months) will be derived from the Kaplan Meier estimate and corresponding confidence interval will be derived based on Greenwood formula for variance derivation and on log-log transformation applied on the survivor function.
 
Participants without documentation of death will be censored on the last date the participant was known to be alive.


PFS is defined as the time from randomization date to the date of the first documented tumor progression, determined by BICR assessments (per RECIST 1.1 or RANO), or death due to any cause, whichever occurs first.
	
BICR and investigator assessments will use Response Evaluation Criteria in Solid Tumors (RECIST 1.1), and Response Assessment for Neuro-Oncology (RANO) criteria for primary CNS neoplasms.
 
Participants without a reported progression will be considered to have progressed on the date of their death if no subsequent anti-cancer therapy initiated.
 
Participants who did not progress or die will be censored on the date of the last tumor assessment.
 
Participants who did not have any on study tumor assessments and did not die will be censored on the first dosing date. Participants who started any subsequent anti-cancer therapy and without a prior reported progression will be censored at the last tumor assessment prior to initiation of the subsequent therapy.
 
Time to event distribution will be estimated using Kaplan Meier techniques. Median PFS along with 95% CI will be constructed based on a log-log transformed CI for the survivor function. Rates at some fixed time points (6, 12, 18 and 24 months) will be derived from the Kaplan Meier estimate and corresponding confidence interval will be derived based on Greenwood formula for variance derivation and on log-log transformation applied on the survivor function.

10.3.2 Safety Analyses

Endpoint Definition	Statistical Analysis Methods

Primary
	
Not applicable

Endpoint Definition	Statistical Analysis Methods
Secondary	
Safety and tolerability	
Descriptive statistics of safety will be presented using the National Cancer Institute (NCI) Common Terminology Criteria for Adverse Events (CTCAE) version 5.0 by tumor types. All on-study AEs and SAEs and drug-related AEs and SAEs will be tabulated using worst grade per NCI CTCAE version 5.0 criteria by system organ class and MedDRA preferred term.
 
On-study lab parameters including hematology, coagulation, chemistry, liver function and renal function will be summarized using worse grade per NCI CTCAE version 5.0 criteria.

Exploratory	Will be described in the statistical analysis plan finalized before database lock

